### **4.1 Eligibility/Screening**

- 4.1.1 Biopsy diagnostic of KS at any time prior to study entry.
- 4.1.2 Documentation of HIV infection at any time prior to study entry.
- 4.1.3 Chest X-ray to rule out pulmonary KS (must be done within 4 weeks of study entry). Pulmonary involvement must be asymptomatic or minimally symptomatic and not require systemic cytotoxic therapy. Patients with a positive chest x-ray or minimal symptoms suggestive of pulmonary disease will have a chest CT performed at entry.
- 4.1.4 A medical history within 21 days of study entry to include the following information:
  - Previous HIV-related and non-HIV related diagnoses.
  - Complete prior anti-HIV therapy, immune based therapy and prior anti-tumor therapy, including start dates of current anti-HIV therapy.
  - All prescription medications taken within the preceding 2 weeks.
  - A signs and symptoms assessment within 2 weeks prior to study entry, including history of weight change.
  - Complete physical exam including the following: vital signs, height, weight, tumor assessment, and Karnofsky performance (Appendix IV) status.
- 4.1.5 Laboratory studies must be obtained within 21 days (unless noted otherwise) prior to study entry, and will include the following:
  - Complete blood count with differential and platelets.

- Serum chemistries: liver enzymes (SGOT, SGPT, alkaline phosphatase), BUN, creatinine, electrolytes, amylase, bilirubin [direct and indirect]), phosphate, and 25-hydroxyvitamin D.
- Urine phosphate, creatinine for calculation of fractional excretion of phosphate ( $FE_{PO_4}$ ). Calculate the  $FE_{PO_4}$  using the formula  $[\text{Ur}_{PO_4} \times P_{Cr} \times 100] \div [P_{PO_4} \times \text{Ur}_{Cr}]$ .  $\text{Ur}_{PO_4}$ = Urine phosphate;  $\text{Ur}_{Cr}$  = Urine creatinine,  $P_{PO_4}$ =Plasma Phosphate  $P_{Cr}$  = Plasma creatinine.

4.1.5.1 If  $FE_{PO_4} > 5\%$  or serum phosphate is low, then 25-hydroxyvitamin D should be drawn at next visit.

- For women of child bearing potential, a serum beta HCG pregnancy test within 72 hours of study entry.
- CD4 count within 4 weeks prior to study entry.
- HIV-1 plasma RNA within 4 weeks prior to study entry (to be evaluated at local institution).
- Stool tested for occult blood.

4.1.6 KS Tumor assessments may be performed on day 1 prior to receiving study medication, but may be performed no earlier than within 2 weeks prior to initiating treatment. Tumor measurements should include the following:

- Identify marker lesions: Select five bi-dimensionally measurable marker lesions for assessing changes in lesion dimension. Select the largest lesions with clearly defined margins. If possible, marker lesions will be photographed. Additionally, the patient will need three lesions greater or equal to 5 x 5 mm that are accessible for 4 mm punch biopsy.
- For patients with < 50 total skin and oral lesions, all lesions must be evaluated for changes in number and characteristics. For patients with  $\geq 50$  total skin and oral lesions, choose three representative areas, if possible, for evaluating change in lesion numbers and characteristics (preferably an area with  $\geq 5$  lesions).

NOTE: A representative area is a single extremity (the back, chest, or face) that has lesions similar in characteristics, i.e., nodularity, size, color, and number, to those found on other parts of the body. A representative area does not need to be the area with the largest number of lesions, but should contain lesions that are truly representative of those throughout the remainder of the body.

- 4.1.7 Staging Criteria: KS staging will be based on the modified ACTG Oncology Committee Staging Criteria (see Appendix V).
- 4.1.8 Specimens for the AIDS and Cancer Specimen Resource (ACSR) to be collected within 28 days prior to study entry (see Appendix VIII for specimen handling), if consent obtained (see Appendix VII).

## **4.2 Evaluations During Treatment**

Evaluations may occur up to 7 days before or after the end of the study visit indicated. Each cycle will be 28 days. Evaluations will continue as outlined below. Patients on the 6-month extension arm will also follow the outline below.

- 4.2.1 Clinical assessment on Days 1, 8, 15, 29 and then every 28 days thereafter, to include an assessment of the following, at every visit (unless otherwise specified):
  - 4.2.1.1 KS tumor assessment at baseline (to be performed on Day 1 prior to receiving study medication, but no earlier than 2 weeks prior to initiating treatment) Day 29, Day 56 and every 2 months thereafter (see Section 4.1.6).
  - 4.2.1.2 A complete physical exam including: vital signs, weight, Karnofsky performance status (Appendix IV) and toxicity evaluation (Days 8, 15, 29 and then every 28 days thereafter).
  - 4.2.1.3 Signs and Symptoms Review.
  - 4.2.1.4 Complete blood count with differential and platelets.
  - 4.2.1.5 Serum chemistries: liver enzymes (SGOT, SGPT, alkaline phosphatase), BUN, creatinine, electrolytes, amylase, bilirubin (direct and indirect, if total is elevated) and phosphate.
  - 4.2.1.6 Urine phosphate and urine creatinine for calculation of fractional excretion of phosphate ( $FE_{PO_4}$ ). [Fractional excretion of phosphate=(spot urinary phosphate/serum phosphate)/(spot urinary creatinine/serum creatinine) × 100].
    - 4.2.1.6.1 If  $FE_{PO_4} > 5\%$  or serum phosphate is low then 25-hydroxyvitamin D should be drawn at next visit or within 7 days (whichever is sooner).
  - 4.2.1.7 For women of childbearing potential: serum  $\beta$ -HCG at any time pregnancy is suspected.
  - 4.2.1.8 All HIV-related and AIDS-defining events (Appendix III) and concomitant medications.

- 4.2.2 CD4 count at baseline, Day 29 and every 3 months thereafter.
- 4.2.3 HIV-1 plasma RNA at baseline, Day 29 and every 3 months thereafter (to be evaluated at local institution).
- 4.2.4 HHV-8 Viral Load- Day 1 and Day 15 of cycle 1, and on Day 1 of cycles 3, 5, 7, 9, 11 (see Appendix XIII).
- 4.2.5 HHV-8 Viral Gene Expression- Day 1 and Day 15 of cycle 1, and on Day 1 of cycles 3, 5, 7, 9, 11 (see Appendix XIII).
- 4.2.6 Biologic Endpoints - Biopsies will be performed at baseline (two), at Day 8 and at time of progression. One biopsy will be performed at baseline and at time of progression or treatment discontinuation for receptor mutation analysis. The DNA from these biopsies will be used to assess exons 12 and 18 in PDGDR  $\beta$ , and exons 11 and 17 in c-kit for mutations that may activate the target receptors or confer resistance to imatinib. If mutations are now found in these exons, we will sequence other exons in which activating mutations have been described. Additionally, RNA from these biopsies will be stored for sequencing cDNAs and accessing expression of downstream targets. These biopsies will be fresh biopsies stored in RNAlator storage media (see Appendix X). Two more biopsies will be performed at baseline and on Day 8 for receptor phosphorylation. These biopsies will assess inhibition of PDGF receptor and will be performed on each specimen. These biopsies will be fixed in 10% formalin (see Appendix X). Serum and plasma specimens for cytokine profiles will be taken at baseline, Day 8 and Day 29 (see Appendix XI). DNA and RNA from PBMCs in these specimens will be stored. The DNA will be used to determine if PDGF-R and c-kit mutations are present in circulating PBMCs, which are infected with KSHV or are restricted to the KS lesions. The RNA will be used for accessing the effect of PDGF-R and c-kit inhibition on the expression of cytokines and other potential downstream targets.
- 4.2.7 Pharmacokinetics - The first 12 patients will have PK sampling performed on Days 1 and 15. Samples will be collected on both days on the following schedule: 0 (immediately prior to patient taking meds for that day), 0.5, 1, 2, 3, 4, 8 and 24 (immediately prior to the next day's dose) hours (see Appendix XII). These data will be compared with historical PK data acquired at the same time points in normal volunteers.

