### 1.2 **Biologic/Correlative Studies**

#### 1.2.1 Expression/Activation (phosphorylation) imatinib kinase targets and signaling intermediates.

We will determine by immunohistochemistry the expression and phosphorylation status of PDGF-R in biopsies from baseline and 8 days. In our initial study, we did not anticipate the degree of pathologic regression after 4 weeks of therapy. The marked decrease in KS spindle cells after 4 weeks of therapy not only resulted in the qualitative decrease in the phospho-PDGF-R staining but also resulted in a quantitative decrease in the cell population that was immunoreactive initially. In order to more accurately quantitate the effect of imatinib on the phosphorylation state of our targets we will examine biopsies at an earlier time point. We decided to biopsy patients at 8 days because the  $t_{1/2}$  of imatinib is ~18 hours and the  $t_{1/2}$  of its metabolite, CGP-74588, is ~36 hours and patients should reach steady state concentration after seven days. We have validated phosphospecific antibodies by immunohistochemistry for all of these determinants except c-Kit receptor.

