### 12.2 Statistical Analysis Plan

Summary statistics will be used to describe the study population (such as ranges, medians of age, gender, baseline performance characteristics). The binomial and its exact 95% confidence interval will be used to estimate clinical response rate. A two-sided one-group chi-square test will be performed to detect a 50% response rate. Due to a small sample size, exact logistic regression may be used to evaluate the effect of baseline characteristics and other covariates with the clinical response. To evaluate inhibition of PDGF receptor, we will

correlate the presence or absence of c-kit and or PDGF-R mutations with clinical response to imatinib by performing chi-square tests or Fisher's exact tests. The cytokine/chemokine profile at baseline, 1 week and 4 weeks after of imatinib therapy will be analyzed using the proteomics approach. The concentration of each cytokine from the samples will be estimated. Friedman's test will be used to evaluate changes between time points with respect to cytokine levels. If a significant difference is detected, the Wilcoxon rank sum test will be used for pairwise comparisons. Exact logistic regression analysis will be used to detect any correlation between baseline concentrations and clinical responses. PK parameters including AUC,  $C_{max}$  and elimination half-life of imatinib will be estimated in the first 12 patients. PK parameters including AUC,  $C_{max}$  and elimination half-life of selected antiretrovirals may be estimated in selected patients. Summary statistics will be used to describe PK results. The incidence of specific AEs will be summarized by severity grade. The binomial proportion and its 95% confidence interval will be used to estimate the proportion of patients who experience an AE of severity Grade 3 or higher. The proportions of primary and secondary resistance to imatinib therapy will be estimated. Chi-square tests or Fisher's exact tests will be used to evaluate associations between c-kit and PDGF-R mutations with resistance to imatinib therapy.

Cluster analyses are planned for the real-time QPCR data. To evaluate the associations between single genes and response, categorical data analysis methods are proposed. If feasible, a multivariate model relating gene expression to response will be performed.

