## **APPENDIX IX: PUNCH BIOPSY**

### **EXPRESSION/ACTIVATION (PHOSPHORYLATION) IMATINIB TARGETS AND SIGNALING INTERMEDIATES**

#### **A. METHODOLOGY**

- A.1** Biopsies will be performed with a 4 mm punch biopsy at baseline and Day 8 of treatment. Fixed tissue samples in formalin will be received from trial sites. They will be embedded in paraffin blocks with an orientation that allows for sectioning perpendicular to the skin surface. Staining of slides will be batched in order that pre and post sections are stained at the same time to control for variability. Two ribbons of four to five tissue sections 5 um thick will be placed one below the other on ProbeOn Plus slides (Fischer). The two ribbons will be treated identically except the top ribbon will receive the primary antibody and the bottom ribbon, which is serving as a negative control, will not. Slides will be stained using the following antibodies: LANA, anti-PDGF-R and anti-phospho-PDGF-R (Tyrosine 783) (Cell Signaling, Beverly, MA). H&E stains will also be performed on all pre and post specimens.
- A.2** Within 48 hours of sectioning, slides will de-paraffinized in xylene and ethanol. Antigen retrieval will be performed by boiling the slides for 10 minutes in pH 6 citrate buffer followed by 10 minutes in 3% H2O2. The slides for phospho-PDGF-R require 15 minutes in 1mM EDTA, pH 8.0 prior to H2O2. The slides are then incubated overnight with the primary antibody at a 1/100 dilution for anti-PDGF-R, a 1/100 dilution for anti-LANA, and a 1/50 dilution anti-phospho-PDGFR at 40C. The slides are then incubated for 30 minutes with 100 µL of biotinylated anti-rabbit secondary antibody, then for 30 minutes with ABC avidin/biotin (Vector Labs, Burlingame, CA) with washes in after each incubation. Slides were incubated in ethanol and xylene prior to mounting coverslips.

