- A.3** All slides will be assigned a random numerical identifier and will be presented in a blinded fashion to two pathology reviewers (Drs. [name] and [name]). Based on review of the slides from the pilot study, it was determined nearly all of the KS spindle cells stained uniformly positive with minimal heterogeneity, and after treatment their immunoreactivity decreased uniformly. Staining intensity of basal keratinocytes is reduced after treatment with imatinib, precluding using them as an internal standard for assessment of lesional cell staining intensity in post-treatment samples. Immunoreactivity of lesional KS cells will thus be scored on a scale of 0 to 5+ by two pathologists, with 0 being the negative control staining of basal keratinocytes and 5+ being equal to the staining intensity of basal keratinocytes in pretreatment samples, and a final score for each sample based on the average of 4 sections.

**A.4** Analysis: Immunohistochemical methods are amenable to statistical assessment. For instance, even using an activation specific antibody, Weber and his colleagues have been able to statistically correlate erk1/erk2 activation with tumor grade and stage of prostate cancer [52]. In this study we will classify the activation of PDGF-R as low (score of 0, 1+ or 2+) or high (score of 3+, 4+ or 5+). The breakpoint for this grouping is based on our observations of degree of inhibition in the pilot trial. Biopsy pairs that score as high at baseline and low at seven days will be considered PDGF-R inhibited, and those that score as high at baseline and high at seven days will be considered PDGF-R not inhibited. Pairs that score low at baseline will be omitted from the analysis. For the purposes of Aims 2 and 3, clinical response is defined as partial or complete response and non-response will be classified as stable disease or disease progression. Our a priori hypothesis is that inhibition of PDGF-R at 7 days correlates with clinical response. A chi 2 test will be used to test whether phosphorylation of PDGF-R (low or high) at 7 days predicted clinical response.

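### The 7-day visit allowance in Section 4.2 covers the Day 8 phosphorylation biopsy, so a compliant specimen can precede the steady state for which Day 8 was chosen

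*Combined protocol and SAP*

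**What the plan says.** Section 4.2 begins with a rule for all on-treatment evaluations: "Evaluations may occur up to 7 days before or after the end of the study visit indicated". Item 4.2.6 of the same section schedules the research specimens: "Two more biopsies will be performed at baseline and on Day 8 for receptor phosphorylation", and "Serum and plasma specimens for cytokine profiles will be taken at baseline, Day 8 and Day 29". Appendix IX A.1 repeats the nominal day for the biopsy: "Biopsies will be performed with a 4 mm punch biopsy at baseline and Day 8 of treatment". None of these places sets a narrower window or an exemption, and neither do the Schedule of Events (Appendix I), the biopsy log in Appendix X, or Appendix XI.

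Section 1.2.1 gives two reasons for a biopsy at Day 8. The first is pharmacokinetic: "patients should reach steady state concentration after seven days". The second is that the 4-week pilot biopsies had lost many of the spindle cells in which phosphorylation was to be measured, so "we will examine biopsies at an earlier time point".

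Appendix IX A.4 then fixes the analysis to that day: "Biopsy pairs that score as high at baseline and low at seven days will be considered PDGF-R inhibited". Pairs that stay high count as not inhibited, pairs that start low are dropped, and inhibition is tested against clinical response with a chi-square test. For cytokines, Section 12.2 describes the early sample as a 1-week sample and states: "Friedman's test will be used to evaluate changes between time points with respect to cytokine levels".

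**The concern.** The general allowance and the reason for the time point pull against each other. A visit window of a week either side is workable for monthly safety visits, but here it is as long as the interval being measured. At its early edge the on-treatment biopsy falls on the same day as the first dose.

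What is at stake is the first-listed secondary objective (2.2.1), inhibition of the PDGF receptor. Each patient contributes one binary classification from one pair of biopsies. If a specimen is taken before drug exposure is established, a patient whose receptor would have been inhibited at seven days may score high and be counted as not inhibited. Such errors would tend to weaken any association with response. Appendix IX A.4 has no rule for a pair whose second biopsy was taken on another day.

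**Working it through.** **Inputs.** Window: 7 days either way (4.2). Nominal day: 8 (4.2.6, Appendix IX A.1). Half-life of imatinib: about 18 h (1.1.1 and 1.2.1). Half-life of the metabolite: about 36 h (1.2.1) or 40 h (1.1.1); both are carried through. The first dose is on Day 1, so Day d lies (d - 1) × 24 h after it.

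**Permitted range.** 8 - 7 = Day 1, and 8 + 7 = Day 15. That is 0 to 14 days of dosing for a nominal 7.

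**The plan's own figure first.** The fraction of steady state at time t with half-life T is 1 - 2^(-t/T). At seven days, t = 168 h:
- imatinib: 168/18 = 9.33 half-lives, 99.8%;
- metabolite, 36 h: 168/36 = 4.67 half-lives, 96.1%;
- metabolite, 40 h: 168/40 = 4.20 half-lives, 94.6%.

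The statement that steady state is reached after seven days is sound.

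**The same formula across the window.**

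| Day | Hours | Imatinib, % | Metabolite, % (40 h to 36 h) |
|---|---|---|---|
| 1, before dosing | 0 | 0 | 0 |
| 2 | 24 | 60 | 34-37 |
| 4 | 72 | 94 | 71-75 |
| 6 | 120 | 99 | 88-90 |
| 7 | 144 | 99.6 | 92-94 |
| 8 | 168 | 99.8 | 95-96 |
| 11 | 240 | 100 | 98-99 |
| 15 | 336 | 100 | 99.7-99.8 |

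**Share of the window that is early.** The metabolite reaches 90% of steady state at T × log2(10) = 3.32 T, which is 119.6 h (T = 36) or 132.9 h (T = 40). Against a window of 336 h, this is 119.6/336 = 36% to 132.9/336 = 40%. These are shares of the permitted time, not forecasts of how many specimens would be taken then.

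**Scale of the analysis, as an illustration.** In the pilot (1.1.5), 4 of 10 patients had evaluable pairs. If that rate recurred (an assumption; those pairs were taken at 4 weeks), 22 to 30 patients would give about 0.4 × 22 = 9 to 0.4 × 30 = 12 pairs. Take 10 pairs, with 5 responders all inhibited and 5 non-responders all not inhibited. Fisher's exact two-sided p is 2/C(10,5) = 2/252 = 0.008. If one inhibited responder is scored as not inhibited, p = 2 × 5/C(10,4) = 10/210 = 0.048. If two are, p = 2 × 10/C(10,3) = 20/120 = 0.17. With so few pairs, one or two errors matter. The documents do not say whether any would occur.

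**The case against.** The strongest reply is that the window does not defeat the choice of Day 8. From about Day 6 to Day 15 the metabolite is at roughly 88-90% of steady state or more, and that is about 60% of the permitted time. Imatinib itself is at 94% by Day 4. Section 1.1.1 gives a peak within 2 to 4 hours of a dose and only 1.5- to 2.5-fold accumulation, so even one dose gives real exposure. All of this stands. It confines the pharmacokinetic problem to the first days of the window, and a Day 1 specimen is drug-free only if taken before the first dose.

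A reader might infer that early specimens do misclassify patients. The documents give no relation between plasma level and PDGF-R phosphorylation, so this is possible but not shown.

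A reader might also infer that a Day 15 biopsy brings back the cell loss. Section 1.2.1 reports that loss at 4 weeks and says nothing about Day 15. Section 1.2.2.2 mentions diarrhea at 2 to 3 weeks that coincided with the onset of response in some patients, but that is not biopsy evidence.

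Nor does the rationale in 1.2.1 extend to the cytokine sample. It concerns the biopsy only, and the planned analysis of baseline cytokines against response does not use the Day 8 sample. The overlap of the Day 8 and Day 15 windows has no consequence either, because no biopsy or cytokine sample is due on Day 15.

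Finally, sites may in practice keep close to Day 8, and specimen labels carry the collection date and time. Off-day specimens could therefore be found afterwards. What is missing is a limit on them and a rule for analyzing them.

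**Conclusion.** The point holds, mainly for the biopsy and mainly at the early side of the window. The allowance is stated without exception, it covers item 4.2.6, and it permits a specimen well short of the condition that Section 1.2.1 set: 34-37% of metabolite steady state on Day 2 and 71-75% on Day 4, against 95-96% on Day 8. Such specimens may misclassify inhibition and dilute its association with response. Specimens near Day 15 meet the steady-state condition but lie closer to the 4-week cell loss. For cytokines what remains is a mismatch with the 1-week label in Section 12.2 and an early edge that touches baseline.

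Only secondary endpoints are affected; the primary response test and the two-stage design are not. The change should be made because it is cheap and the contradiction is the plan's own. The accumulation figures assume first-order kinetics, regular dosing from Day 1 and the documents' half-lives. They ignore any lag in forming the metabolite, which favors the protocol.

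**What to change.** In Section 4.2, except the Day 8 biopsy from the 7-day allowance and, for consistency, the Day 8 cytokine sample. Give both a narrow window that opens no earlier than Day 7, for example Day 7 to Day 11. At Day 7 imatinib is at 99.6% and the metabolite at 92-94% of steady state, so one early day costs little.

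The width should respect the shipping sections of Appendices IX and XI, which ask outside sites to schedule these visits Monday to Wednesday. The days without a standard visit, Thursday to Sunday, number four, so any five consecutive days include a Monday, Tuesday or Wednesday. A three-day window of Day 8 to Day 10 would not: with Day 1 on a Thursday it runs Thursday to Saturday.

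In Appendix IX A.4, base the main analysis on in-window pairs, identified from the recorded collection date, and add off-window pairs only in a sensitivity analysis.

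The cost is a sentence in each place, less scheduling flexibility for one visit, and possibly a few pairs moved to the sensitivity analysis.

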#### 1.2.2.1 Receptor Mutation Analysis

Mutations of c-kit and PDGF-R have been shown to play a role in tumorigenesis and imatinib resistance. Activating mutations of c-Kit have been reported in mastocytosis, acute myelogenous leukemia, GISTs, myeloproliferative disorders (MPD) and sinonasal lymphomas. In vitro studies suggest activating mutations in the kinase domain of c-Kit are resistant to inhibition by imatinib. Additionally, activating mutations in the kinase domain of PDGF-R  $\alpha$  have been reported in GISTs. We will correlate the presence or absence of c-Kit and/or PDGF-R mutations with clinical response to imatinib.

As the experience with imatinib therapy for CML increased, it became clear that some patients who initially responded later relapsed. Studies demonstrated multiple mechanisms of resistance including over-expression of BCR/ABL transcripts, acquisition of new chromosomal abnormalities and mutation of the kinase domain. In one study, mutations of the kinase domain appeared to be the mechanism of resistance in 23 of 43 cases. At the time of discontinuation, we will biopsy a lesion that is clearly growing or has not responded and sequence PDGF-R and c-Kit.

If any novel mutations are found in either of these cases, we will determine in vitro whether they are activating mutations and/or resistant to imatinib.

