### **2.2 Secondary Objectives**

2.2.1 Evaluation of inhibition of PDGF receptor as determined by immunohistochemistry.

2.2.2 Evaluation of cytokine profiles pre and post imatinib therapy.

2.2.3 Evaluation of pharmacokinetic profile of imatinib and antiretrovirals in HIV patients.

2.2.4 Evaluation of mechanisms of primary and secondary resistance to imatinib therapy.

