## **APPENDIX X: PUNCH BIOPSY**

### **RECEPTOR MUTATION ANALYSIS**

#### **A. METHODOLOGY**

Each patient will have a 4 mm punch biopsy performed at baseline and at the time of progression or treatment discontinuation of a representative lesion. RNA and genomic DNA will be isolated from samples. PCR primers for the genomic DNA were designed to begin in the flanking introns and cover the entire exon being studied. The PCR products will be gel purified and will then be subcloned into PCR4blunt-TOPO vector. The ligated vectors for each exon will then be used to transform competent E. Coli XL1 blue and the bacteria will be plated and grown overnight. Single colonies will be picked and then mini-prepped. The DNA from the mini-preps will be sequenced. Because the malignant cells of KS will only be a portion of the biopsy, the heterogeneity of the tumor must be taken into account before we can declare a negative result. Based on our previous studies we estimate that approximately 50% of a 4 mm punch biopsy is composed of KS spindle cells which express PDGF-R  $\beta$  and c-kit. If only one allele of the KS spindle cell has a mutation and the ratio of normal to mutant cells is one to one, only one out of four exons carry the mutation. To calculate the number of sequences to perform on each exon to assure a mutation was not missed, we first decided level of 95% confidence level was acceptable. The number of assays required is the number of times the negative result (normal sequence) must happen to be less than or equal to 5% (100% -95%). Mathematically this can be solved as a probability problem.

$$(p \{\text{normal sequence}\})^n < 0.05 \quad \text{where } n \text{ is number of assays and } p(\text{normal sequence}) = 0.75$$

$$\text{This transforms to } (0.75)^n < 0.05 \rightarrow n \log(0.75) < \log(0.05) \rightarrow n(-0.125) = -1.301 \\ n = 10.41 \rightarrow 11$$

Thus to achieve a 95% confidence of not missing a mutation each exon will be sequenced 11 times. If a positive mutant clone is discovered, it is possible that the mutation is an error introduced by PCR. We are using PFU polymerase, which has a lower mistake rate than Taq polymerase to reduce the incidence of mistakes. Because PFU still has a mistake rate of 1 in 10,000 nucleotides all mutants will have to be confirmed by two more clones from different PCR reactions to be considered a positive result. If mutations are present, we will determine if they correlate with non-response.

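### Section 4.2.6 triggers sequencing of further exons on a positive result ('now found'), almost certainly a slip for 'not found' that no other section corrects

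*Combined protocol and SAP*

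**What the plan says.** Section 4.2.6 (under 4.2, Evaluations During Treatment) has DNA from the baseline biopsy and the progression or discontinuation biopsy examined at PDGF-R beta exons 12 and 18, "and exons 11 and 17 in c-kit for mutations that may activate the target receptors or confer resistance to imatinib". The rule for going further follows at once: "If mutations are now found in these exons, we will sequence other exons in which activating mutations have been described". The next sentence adds that "RNA from these biopsies will be stored for sequencing cDNAs and accessing expression of downstream targets".

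Appendix X, part A, fixes how thoroughly each exon is read: "Thus to achieve a 95% confidence of not missing a mutation each exon will be sequenced 11 times". It does not mention a second set of exons or what would prompt one.

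Section 1.2.2.1, in the background, says that at discontinuation "we will biopsy a lesion that is clearly growing or has not responded and sequence PDGF-R and c-Kit", without naming exons.

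The results serve secondary objective 2.2.4, "Evaluation of mechanisms of primary and secondary resistance to imatinib therapy". Section 12.2 will "correlate the presence or absence of c-kit and or PDGF-R mutations with clinical response to imatinib", using chi-square or Fisher's exact tests, and will test the association between mutations and resistance in the same way. It does not define 'absent'.

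**The concern.** A stepwise mutation search should widen after a negative first step, because that is where mutation status is still open. The printed rule does the reverse. It reads more exons in patients already known to carry a mutation, whose presence/absence status cannot change, and none in patients without one.

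This is the operational instruction that a laboratory would follow. If it were followed as printed, a carrier whose only mutation lies outside the four exons would enter the mutation-absent group in both association tests of Section 12.2. If such misses were unrelated to outcome, they would weaken any real association. The documents do not show that they would be unrelated, so the direction of the error is itself an assumption.

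**Working it through.** **Inputs from the documents.** Four first-line exons and the trigger wording (4.2.6); probability 0.75 that a clone reads normal when one allele of the spindle cells is mutated, since "only one out of four exons carry the mutation" (Appendix X); 11 clones per exon (Appendix X); 22 evaluable patients (12.1).

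**Inputs not in the documents, so assumed.** Mutation prevalence, 10% to 30%. The share *f* of carriers whose mutation lies only outside the four exons, 0 to 0.50.

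**1. The plan's own figure.** n = log(0.05)/log(0.75) = 10.41, rounded up to 11. The miss probability is 0.75^11 = 0.0422 (with 10 clones it would be 0.0563), so detection is 1 - 0.0422 = 0.9578. The figure reproduces. It applies only to an exon that is sequenced; an exon that is not read has a detection probability of zero.

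**2. What each wording does.**

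| Result in the four exons | 'now found' (as printed) | 'not found' (as presumably meant) | Can further exons change presence/absence? |
|---|---|---|---|
| Mutation found | Other exons read | Other exons not read | No, already present |
| None found | Other exons not read | Other exons read | Yes |

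**3. Possible size under the printed wording.** Sensitivity per carrier = (1 - f) × 0.9578. Under the intended wording it is 0.9578 for every f, provided each relevant further exon is also read with 11 clones. Expected carriers called absent = 22 × prevalence × (1 - sensitivity).

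| f | Sensitivity as printed | Missed of 22, prevalence 10% | Missed of 22, prevalence 30% |
|---|---|---|---|
| 0 | 0.958 | 0.09 | 0.28 |
| 0.10 | 0.862 | 0.30 | 0.91 |
| 0.25 | 0.718 | 0.62 | 1.86 |
| 0.50 | 0.479 | 1.15 | 3.44 |
| Intended trigger, any f | 0.958 | 0.09 | 0.28 |

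Example: 22 × 0.30 × (1 - 0.479) = 3.44. At f = 0 the two wordings give the same result, and what remains is the clone-sampling miss that Appendix X already accepts. The largest excess due to the wording is 3.44 - 0.28 = 3.16 patients.

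**4. Is the trigger stated correctly elsewhere?** Appendix X sets depth per exon, not which exons follow. Section 12.2 uses mutation status without saying which exons must be negative. The RNA sentence in 4.2.6 stores material but gives no trigger or exon list. Section 1.2.2.1 describes sequencing at discontinuation in general terms, with no exon list or sequence of steps. None supplies a competing rule.

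**The case against.** The strongest reply is that this is a one-letter slip that nobody would follow. That is very probably right about intent. Appendix X takes care over when a negative result may be declared, which fits only 'not', and Section 4.2.6 contains other slips of the same kind. The letter may even be an artefact of text extraction, so it is worth checking on the PDF page. What survives is that the printed instruction is wrong and no other section corrects it.

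Three stronger readings might be inferred, and the documents do not support them.

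- *Patients with no mutation found are never searched further and are misclassified.* Only carriers of a mutation solely outside the four exons could be misclassified. RNA is stored for cDNA sequencing, and Section 1.2.2.1 speaks of sequencing both receptors at discontinuation without an exon limit. Since Section 12.2 leaves 'absent' undefined, absence in the four named exons is a usable definition if it is reported as such.
- *Correcting the word to 'not' still contaminates the groups, because a baseline mutation that persists at progression would block the search for an acquired one.* That patient is 'present' whether or not a second mutation is found, so nobody changes group in a presence/absence test. What is lost is descriptive detail about acquired resistance.
- *Both biopsies of each pair must therefore have extended sequencing.* A rule triggered whenever no newly acquired mutation is found would apply to most pairs and come close to routine extended sequencing, at 2 × 11 = 22 clones per additional exon per pair. The documents do not require this.

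**Conclusion.** The point holds as a minor error: the trigger in Section 4.2.6 is wrong as written and is not put right elsewhere. If followed literally, it would leave some carriers recorded as mutation-absent by the DNA step in two secondary analyses, mutation against response and mutation against resistance.

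The number is unknown. The range of about 0.1 to 3.4 of 22 rests wholly on the assumed prevalence and outside share, on one detectable mutation per carrier at the one-in-four clone frequency of Appendix X, and on usable biopsies from all 22 patients. It applies only to the literal reading, and its lower end is not due to the wording at all. The primary response endpoint, the two-stage rule and the sample size are untouched. Nothing suggests that the reversed search was an intended design choice.

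**What to change.** 1. In Section 4.2.6, replace 'now' with 'not' in the sentence that triggers further sequencing.
2. Repeat the trigger in Appendix X, part A, next to the 11-clone rule, and preferably list the further exons there so that the laboratory has one complete instruction.
3. In Section 12.2, state that 'mutation absent' will be reported by the exons actually sequenced.

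The cost is one word and two or three sentences. No extra biopsy is needed, and there is no sequencing beyond what the 'not' reading already implies: 11 clones per further exon in each biopsy that is negative in the first four. Reading the same exons at baseline and progression would be an optional descriptive addition for acquired resistance; this point does not depend on it.
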